APPENDIX

Appendix 1 - Columbia-Suicide Severity Rating Scale (C-SSRS), "Screening" and "Since Last Visit"	52
Appendix 2 – Fagerström Test for Nicotine Dependence (FTND).....	58
Appendix 3 – Smoking History	59
Appendix 4 – Other Nicotine Use Questionnaire.....	60
Appendix 5 – Modified Cigarette Evaluation Questionnaire – Extended (mCEQE)	61
Appendix 6 – Reasons to Smoke	63
Appendix 7 – Shiffman Jarvik Withdrawal Scale.....	64

Appendix 8 – Minnesota Nicotine Withdrawal Scale 66

FIGURES

Figure 1 - Overall Study Design and Plan, 7-Week Treatment Period 16

TABLES

Table 1 - Clinical Chemistry.....	25
Table 2 - Hematology.....	25
Table 3 - Serum Pregnancy	25
Table 4 - Urinalysis	25
Table 5 - Drug Screening	26
Table 6 - Schedule of Event.....	34

EXPLANATION OF TERMS

The following special terms are used in this protocol:

Baseline Visit	The baseline visit for this study is defined a V2.
Baseline Value	The baseline value is defined as the value at V2 unless otherwise specified.
End of Study	The end of study (EOS) for a subject is defined as the date of safety follow-up or the date of early termination of the subject.
Combustible cigarette	The term 'combustible cigarette' (CC) refers to commercially available, combustible cigarettes and excludes hand-rolled cigarettes, cigars, pipes, bidis, and other nicotine containing products.
Volunteer	A volunteer is an individual who has expressed interest in participating in a clinical research study.
Candidate	Individuals who completed a pre-screening evaluation with a member of the Rose Research Center recruitment team. They have been deemed as pre-qualified to come in for a physical screening visit to determine further eligibility.
Participant	A volunteer who has signed the study consent form. Once an individual signs the study consent form and receives a participant number, they are considered a Participant. The term "Subject" can and has historically been used interchangeably with Participant but for the purposes of communication, RRC has adopted the term participant as a global term for this status.

ABBREVIATIONS

5-HT	Serotonin
ADHD	Attention-deficit/hyperactivity disorder
AE	Adverse event
AESI	Adverse event of special interest
ALT	Alanine aminotransferase
AP	Alkaline phosphatase
APMP	Abuse Potential Monitoring Process
AST	Aspartate aminotransferase
BID	Twice daily
BL	Baseline
BMI	Body mass index
BUN	Urea nitrogen
CBP	Childbearing potential
CC	Combustible cigarette
CFR	Code of Federal Regulations

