4.6 DISCONTINUATION OF PARTICIPANTS FROM STUDY

Discontinued participants will include both participants who withdraw from the study (participant's decision) or participants who are discontinued from the study (following Investigator's decision). A participant can only be discontinued from the study after the IMP is dispensed to them. Participants that are not dispensed the IMP are considered screen failures.

Participants will be informed that they are free to withdraw from the study at any time. Participants should be questioned for the reason of premature withdrawal from the study, although they are not obliged to disclose it.

Participants discontinued from the study cannot re-enter the study.

Participants will be discontinued from the study for any of the following reasons:

- Withdrawal of informed consent.
- Any adverse effect or condition that would jeopardize continued safe study participation.
- Discontinuation is considered to be in the best interest for the participant or for other participants participating in the study, as judged by the Investigator or designee.

Participants may be discontinued from the study for any of the following reasons based on the judgment of the Investigator:

- No-show to appointments and unable to reschedule within the visit window.
- The misuse or abuse of study related equipment.
- Potential loss of the participant's data validity.
- Unwilling or unable to comply with study procedures.

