6.5 SAFETY EVALUATIONS AND OTHER ASSESSMENTS

Clinical safety evaluations will be performed to ensure that participants meet the requirements of the study and to monitor participant safety. An overview of all assessments is provided in the schedule of events.

Urine will be collected, and blood will be drawn from each subject prior to treatment with centanafadine. Additional urine and blood samples may be collected for further evaluation of safety as warranted by the investigator's judgment. Reports from the laboratory will be assessed by the investigator or qualified designee for clinical significance.

The results of the clinical chemistry, hematology and urine analysis safety panel will not routinely be given to participants to send or be sent to their physician to include in their medical record. However, if the participant's laboratory results are clinically relevant (including positive pregnancy tests), the research medical staff will send the participant a copy of the laboratory results. Participants who are accepted into the study but need medical follow-up due to minor abnormalities in laboratory results (at any session) will also receive a copy of the laboratory results.

Additional urine and blood samples may be collected for further evaluation of safety as warranted by the investigator's judgment. Reports from the laboratory will be assessed by the investigator or qualified designee for clinical significance.

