6.5.1 Clinical Chemistry

Blood will be collected for Clinical Chemistry tests at the screening visit (V1), V4 and the final study visit (V6).

Clinical Chemistry	
Sodium	Chloride
Potassium	Carbon dioxide
Urea nitrogen (BUN)	Creatinine
Glucose	Calcium
Protein, total	Albumin
Bilirubin, total	Alkaline phosphatase (AP)
Aspartate aminotransferase (AST)	Alanine aminotransferase (ALT)
Glycosylated Hemoglobin (HbA1c; at screening only)	Gamma-glutamyl transferase (GGT)

Table 1 - Clinical Chemistry

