6.5.4 Urinalysis

A urine sample will be collected for Urinalysis at the screening visit (V1) and the final study visit (V6).

Urinalysis	
pH	Glucose
Red blood cell traces	Specific gravity
Bilirubin	Nitrite
Protein	WBC Esterase

Table 4 - Urinalysis

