6.6.6 Final Study Visit (V6) – 7 weeks on IMP

Seven weeks (\pm 3 days) after starting the study drug, participants will return to the Center for V6 to complete questionnaires and assessments. Participants will also be asked to return all unused IMP.

The sequence of the following questionnaires and assessments will be at the discretion of the Investigator (or designee).

6.6.6.1 **Questionnaires**

- Other Nicotine Use Questionnaire
- Modified Shiffman-Jarvik Withdrawal Scale
- Modified Cigarette Evaluation Questionnaire Extended (mCEQE)
- Minnesota Withdrawal Questionnaire
- Fagerström Test for Nicotine Dependence

6.6.6.2 **Assessments**

- Review of Concomitant Medication
- Review of Concomitant Disease
- Expired air CO breath test
- Alcohol breath test
- Urine collection for urinalysis and pregnancy (all participants with the potential to become pregnant)
- Blood collection for safety laboratory testing, pharmacokinetics, and future biospecimen research (for those participants who consented to this optional collection)
- Vital signs (systolic and diastolic blood pressure, pulse rate, and respiratory rate), will be measured in sitting position after the participant has rested for at least 5 minutes.
- Weight
- Temperature
- Electrocardiogram (ECG) -- A standard 12-lead ECG will be recorded after the participant has rested for at least 5 minutes in a supine position.
- Columbia-Suicide Severity Rating Scale (C-SSRS)
- Review of adverse events (as needed)

- Physical examination (as needed)

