6.8 SCHEDULE OF EVENTS

Study Week	SCR	Wk 0 Baseline		Wk 1 (+ 3 days)	Wk 2 - Wk 3 (± 3 days)	Wk 4 - Wk 5 (± 3 days)	Wk 6 - Wk 7 (± 3 days)	Wk 8 (+ 2 days)
Visit	V1	V2		V3	V4	V5	V6	Safety Follow-up
IMP Timeline		Day -1	Day 1 IMP	Wk 1 IMP	Wk 3 IMP	Wk 5 IMP	Wk 7 IMP	
Informed Consent	x							
Inclusion/Exclusion Criteria	x	x						
Enrollment		x						
Visit Preparation	x	x		x	x	x	x	
Visit Reminder Calls	x	x		x	x	x	x	
Telephone Contact -(Day 1, Wk 2, Wk 4, Wk 6, and 7 day F/U)			x		x	x	x	x
Questionnaires								
Reasons to Smoke		x						
Smoking History	x							
Other Nicotine Use		x		x	x	x	x	x
Registration Form	x							
Medical History with Review of Systems	x							
Modified Cigarette Evaluation Questionnaire Extended (mCEQE)		x		x	x	x	x	x
The Fagerström Test for Nicotine Dependence (FTND)		x						x
Modified Shiffman-Jarvik Withdrawal Scale		x		x	x	x	x	
Minnesota Withdrawal Questionnaire		x		x	x	x	x	x
The Columbia-Suicide Severity Rating Scale (C-SSRS)	x	x		x	x	x	x	
Smoking Status (via daily messages)	x	x	x	x	x	x	x	
Medication Adherence (via daily messages)		x	x	x	x	x	x	
Blood Samples								
Clinical Chemistry	x				x		x	
CBC w/Diff & Platelet Count	x				x		x	
Serum Pregnancy Test*	x							
HbA1c	x							
PK Blood Draws					x		x	
CCI								
Urine Samples								
Urinalysis Safety Panel	x						x	
Drug Screen	x				x	x		
Pregnancy		x		x	x	x	x	
Other Assessments								
Prior and Concomitant Medication Assessment and Medical Review	x	x		x	x	x	x	x
Concomitant Disease Assessment and Medical Review	x	x		x	x	x	x	
CO Breath Test	x	x		x	x	x	x	
ECG	x						x	
Blood Pressure - Sitting and Standing Positions	x	x		x	x	x	x	
Heart rate	x	x		x	x	x	x	
Temperature	x	x		x	x	x	x	
Respiratory rate	x	x		x	x	x	x	
Weight	x	x		x	x	x	x	
Physical Examination (as needed)	x	x		x	x	x	x	
Alcohol Breath Test	x							
Procedures								
AE Interview and Assessment		x		x	x	x	x	x
Collect Used/Unused IP				x	x	x	x	
Dispense IP		x		x	x	x		
IMP Dosing			x	x	x	x	x	

* Serum pregnancy test will be done if urine pregnancy test is positive

Table 6 - Schedule of Event

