9.8 PREGNANCY AFTER ENROLLMENT

During the trial, all FOCBP should be instructed to contact the investigator immediately if they suspect they might be pregnant (eg, missed or late menstrual cycle).

If a subject is suspected to be pregnant before she receives IMP, the IMP administration must be withheld until the results of serum pregnancy tests are available. If the pregnancy is confirmed, the subject must not receive the IMP and must not be enrolled in the trial. If pregnancy is suspected while

the subject is taking IMP, the IMP must be withheld immediately (if reasonable, taking into consideration any potential withdrawal risks) until the result of the pregnancy test is known. If pregnancy is confirmed, the IMP will be permanently discontinued in an appropriate manner (eg, dose tapering if necessary for subject safety) and the subject will be withdrawn from the trial.

The investigator must immediately notify the sponsor of any pregnancy associated with IMP exposure during the trial and for 30 days after the last dose of IMP for female subjects, and for 30 days after the last dose of IMP for partners of male subjects, and record the event on the IRE form and forward it to the sponsor. The sponsor will forward Pregnancy Surveillance Form(s) for monitoring the outcome of the pregnancy.

Protocol-required procedures for trial discontinuation and follow-up must be performed on the subject unless contraindicated by pregnancy (eg, x-ray studies). Other appropriate pregnancy follow-up procedures should be considered, if indicated. In addition, the investigator must report to the sponsor, on appropriate Pregnancy Surveillance Form(s), follow-up information regarding the course of the pregnancy, including perinatal and neonatal outcome. Infants should be followed for a minimum of 6 months from the date of birth, if consent is given to do so.

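### ECG and urinalysis are scheduled on treatment only at V6, with no assessment required at early termination, so dividing abnormality counts by everyone dosed in effect counts untested leavers as normal

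*Protocol*

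**What the plan says.** **Schedule.** In the visit lists (Protocol 6.6.1 to 6.6.6) and Table 6 (6.8), ECG appears at V1 and V6 only. The V6 entry reads "Electrocardiogram (ECG) -- A standard 12-lead ECG will be recorded after the participant has rested for at least 5 minutes in a supine position". Urinalysis is also at V1 and V6 only (Protocol 6.5.4; SAP 9.3 agrees). Chemistry and hematology are drawn at V1, V4 and V6 (Protocol 6.5.1 and 6.5.2). V1 precedes dosing. Blood pressure and pulse are taken at every visit.

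**Early termination.** The protocol expects it. One mandatory reason in section 4.6 is "Any adverse effect or condition that would jeopardize continued safe study participation". The Explanation of Terms says "The end of study (EOS) for a subject is defined as the date of safety follow-up or the date of early termination of the subject". Neither place attaches an assessment, and Table 6 has no early-termination column. Section 9.8, on pregnancy, says "Protocol-required procedures for trial discontinuation and follow-up must be performed on the subject unless contraindicated by pregnancy", but the visible text defines no such procedures. Section 6.5 makes further sampling optional: "Additional urine and blood samples may be collected for further evaluation of safety", on the investigator's judgment. The safety follow-up is a telephone call. Section 9.5, on adverse events of special interest, is redacted and may specify further tests.

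**Analysis.** Under SAP section 9, a participant enters the numerator only with an evaluation that meets the criteria. For ECG and laboratory results the denominator is the Safety Analysis Set, which SAP 5.2 defines as everyone given at least one dose. SAP 9.6 counts ECG abnormalities from scheduled and unscheduled post-baseline visits and summarizes change from baseline at scheduled visits and at the last visit.

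**The concern.** A dosed participant who stops before V6 has no scheduled on-treatment ECG or urinalysis. One who stops before V4 has no scheduled on-treatment chemistry or hematology either. Unless someone orders an extra test, that person is in the denominator and cannot be in the numerator.

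Two things are at stake. The first is the meaning of the printed percentage: a reader will take 4/50 as the rate in 50 people examined, when fewer may have been examined. The second is participant safety: someone withdrawn for an adverse event has no required exit ECG or blood test. The protocol excludes people with prolonged QTcF and users of QTc-prolonging drugs, so it treats cardiac conduction as worth guarding, yet its single on-treatment ECG falls at the visit early leavers do not reach.

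**Working it through.** The plan gives no figure on this point to reproduce, and no drop-out rate for this trial.

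**Inputs**

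- Number dosed: 50 (the planned enrollment, single arm).
- d: the number of dosed participants with no post-baseline test of the type in question. Assumed, with no unscheduled tests: 10-20% stopping before V6 (d = 5 to 10) for ECG and urinalysis; 4-10% stopping before V4 (d = 2 to 5) for chemistry and hematology. Protocol 1.1 cites nearly 10% drop-out due to adverse effects in varenicline trials, which makes the lower V6 value plausible but is not a figure for this drug.
- x: the number with an abnormality. Illustrated with x = 4.

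**Formulas**

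- Reported rate = x/50. Rate among those tested = x/(50 − d).
- Factor (reported ÷ tested) = (50 − d)/50.
- Logical bounds on the all-dosed rate: x/50 if no untested leaver is abnormal, (x + d)/50 if all are.

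**Results for x = 4**

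| Test | d | Factor | Reported | Among tested |
|---|---|---|---|---|
| ECG, urinalysis | 5 | 45/50 = 0.90 | 4/50 = 8.0% | 4/45 = 8.9% |
| ECG, urinalysis | 10 | 40/50 = 0.80 | 4/50 = 8.0% | 4/40 = 10.0% |
| Chemistry, hematology | 2 | 48/50 = 0.96 | 4/50 = 8.0% | 4/48 = 8.3% |
| Chemistry, hematology | 5 | 45/50 = 0.90 | 4/50 = 8.0% | 4/45 = 8.9% |

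For ECG and urinalysis the gap is 0.9 to 2.0 percentage points. The bounds on the all-dosed rate are 8.0% to (4 + 5)/50 = 18.0% with 5 untested, and 8.0% to (4 + 10)/50 = 28.0% with 10 untested. The upper ends are logical limits, not estimates. In both cases the plan prints the lower one.

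**If no abnormality is seen**, the exact one-sided 95% upper limit is 1 − 0.05^(1/n): 5.8% for n = 50, 6.4% for n = 45 and 7.2% for n = 40. A zero reported over 50 therefore looks somewhat more reassuring than the data allow.

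**The case against.** An all-dosed denominator is a recognized convention, and these are descriptive rates in a 50-person single-arm study with no decision rule attached. The shift is also small against sampling error: the exact 90% interval for 4/50 is 2.8% to 17.4%. Both points stand and limit the weight of the finding. They do not change the direction of the error, which more precision would not remove.

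Leavers with a clinical problem are not left to a telephone call alone. Ongoing adverse events are followed until they improve, resolve, stabilize or are explained (Protocol 9.2.1), serious events are followed clinically (9.4), medical staff decide the course of action for side effects (7.5), and laboratory tests may be repeated or added (9.1.6). Unscheduled ECGs count under SAP 9.6. All of this is true, but none of it requires an ECG or laboratory test at exit.

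Three stronger readings are tempting, and the documents do not support them:

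- *That no planned output shows who is untested.* The public list of tables is cut off at CT-12.2, and SAP 9.3 lists all laboratory results, so the number untested can be derived for laboratory tests. What the visible plan lacks is that number beside the rate.
- *That leavers would have more abnormalities, so that a signal is hidden.* The plan does not show whether people who tolerate the drug poorly would be tested more or less often than others, or would have more abnormal results.
- *That one on-treatment ECG is inadequate for this drug.* The common adverse effects in Protocol 7.3.1 include no QT effect, and the Investigator's Brochure is not available here.

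**Conclusion.** The point holds as a limited one. On the visible text, V6 is the only scheduled on-treatment ECG and urinalysis, no assessment is required at early termination, and the SAP denominator includes people who may never have been tested. The reported rates are therefore lower bounds.

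The effect is mainly on ECG and urinalysis, at 0.90-0.80 of the rate among those tested. It is small for chemistry and hematology, at 0.96-0.90. These sizes rest on the assumed stopping rates and on no unscheduled tests; every leaver who is tested brings the factor closer to 1. ECG change from baseline describes essentially those who reach V6, apart from unscheduled recordings. Vital signs share the denominator but are little affected, because they are measured at each visit. Abstinence and nausea results are unaffected. The change should be made because it is cheap and serves participants, not because the main result depends on it.

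**What to change.** 1. **Protocol.** Relabel the V6 column of Table 6 as V6 / Early Termination. Add to 4.6 and 6.6.6 that any dosed participant who stops early is asked to complete the V6 safety assessments (ECG, chemistry, hematology, urinalysis, vital signs, C-SSRS, adverse event interview, return of study drug) as soon as possible, ideally on the last dosing day or within 3 days after it.
2. **Timing rule.** State that the 3 days are a scheduling target, not an exclusion rule. Tests up to the safety follow-up still count toward abnormality incidence, flagged by days since last dose. The 3-day exclusion in footnote b of SAP Table 5.4-1 is headed for efficacy and should not be carried over: it could drop late-detected abnormalities that SAP 9.6 now counts and that Appendix 2 does not restrict to on-treatment values. Appendix 3 does speak of on-treatment values, so say there that these exit ECGs qualify.
3. **SAP 9.6 and 9.3.** Use the exit record as the last visit for ECG, and add the same last-visit summary for laboratory data.
4. **SAP section 9.** Beside the all-dosed percentage, report ECG and laboratory abnormality incidence over participants with at least one post-baseline assessment of that test, and state how many have none.

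The cost is low. The assessments are already planned and are only brought forward for early leavers, and the reporting change is one added line in the SAP. Some leavers, including those lost to follow-up, will not attend, so the gap shrinks but does not close. The tested-only rate may itself be selective, which is why both rates should be shown.

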6.6.7 Telephone Contact

Participants will be contacted via phone on Day 1 (first day of IMP) and on weeks that they are not scheduled to visit the Center (Wk 2, Wk 4, and Wk 6) to ask how they are doing and answer any questions the participant may have.

6.6.8 Safety Follow-Up

Seven to 10 days after V6, participants will be contacted via phone for a safety follow-up.

6.6.8.1 *Questionnaires*

- Other Nicotine Use Questionnaire
- Modified Cigarette Evaluation Questionnaire Extended (mCEQE)
- Minnesota Withdrawal Questionnaire

6.6.8.2 *Assessments*

- Review of Concomitant Medication
- Review of Concomitant Disease
- Review of adverse events

6.7 DAILY MESSAGING

Rose Research Center will utilize eResearch, an IRB approved proprietary mobile electronic application for clinical research studies available in both the iOS and Android app stores. For the purposes of this protocol, the Survey's feature will be utilized to push the daily messages to enrolled participants.

Daily text reminders and/or push notifications may be paired with these daily messages in order to remind participants about the request to complete these assessments.

6.7.1 Daily Message (after screening, prior to V2)

Participants will receive a push notification with a prompt to a daily survey to access the following:

- Have you smoked any combustible cigarettes today?
 - If yes, how many cigarettes did you smoke?

6.7.2 Daily Message (Visit 2 through V6)

Participants will receive a push notification with a prompt to a daily survey to assess the following:

- Have you smoked any combustible cigarettes today?
 - If yes, how many cigarettes did you smoke?
- Did you take your 1st dose of study drug today?
- Did you take your 2nd dose of study drug today?
 - If yes, did you take the 2nd dose 4 to 6 hours after the 1st dose?

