4.9.3 All other visit Windows

Participants may attend sessions up to three calendar days pre or post the scheduled visit.

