The Fagerström Test for Nicotine Dependence is a six-item questionnaire developed by Karl-Olov Fagerström and is used to determine someone’s level of nicotine dependence. The scores obtained on the test allow the classification of nicotine dependence in three different levels: mild (0-3 points), moderate (4-6 points), and severe (7 -10 points).

6.5.16.6 *Smoking History Questionnaire*

The Smoking History is a questionnaire designed to help assess the participant’s current and past smoking habits. This questionnaire will be administered at screening (V1) and will include questions about the number of years participants have smoked combustible cigarettes (CC), the number of CCs per day smoked over the last 12 months, brand of CCs, use of other tobacco products and use of nicotine replacement therapy or other smoking cessation treatments. This questionnaire will also be used to check eligibility criteria.

6.5.16.7 *Other Nicotine Use Questionnaire*

The Other Nicotine Use questionnaire will be used to capture information about the use of nicotine containing products (other than combustible cigarettes). This questionnaire will be given at V2 and all subsequent visits, including safety follow-up.

6.5.16.8 *Minnesota Nicotine Withdrawal Scale (MNWS)*

The MNWS is used to assess nicotine withdrawal symptoms including craving and mood effects. Participants will be asked to assess eight symptoms on a 5-point scale ranging from 0 to 4, where 0 = none, 1 = slight, 2 = mild, 3 = moderate, 4 = severe.

6.5.16.9 *Study Drug Compliance*

Participants will be queried via electronic messages whether they have been compliant with taking the study drug. These messages will commence after the second visit (V2) and continue through the End of Study.

6.5.16.10 *Smoking Status*

Electronic messages will be sent to participants starting after the second visit (V2), through the End of Study, to ascertain the participants smoking status.

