3.1 Type/Design of Trial

This single-group, small-scale, open-label, phase 2 study evaluates centanafadine as a potential smoking cessation treatment. Participants enrolled in the study will be given centanafadine SR at a dose of 400 mg total daily dose (TDD) (200 mg twice daily [BID]) approximately 4 to 6 hours apart for seven weeks. The study consists of a 28-day screening period, a baseline visit, a 7-week treatment period, and a 7-day safety follow-up period. Participants visit the study center a total of 6 times, including a screening visit (V1), baseline visit (V2), a visit one week (+3 days) after starting the study drug (Week 1 visit V3), three weeks (± 3 days) after starting the study drug (Week 3 visit V4), five weeks (± 3 days) after starting the study drug (Week 5 visit V5), and seven weeks (± 3 days) after starting the study drug (Week 7 visit V6). All participants are requested to participate in a 7-day safety follow up period, which will consist of telephone contact seven days (+2 days) after the last dose of investigational medicinal product (IMP).

A schematic of the trial design for this study is provided in [Figure 3.1-1](#).

[figure not shown]

Figure 3.1-1 Trial Design Schematic

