5.4 Trial Visit Window

The actual assessment date is mapped into the trial week based on [Table 5.4-1](#). Trial days are derived from the formula: Trial Day = Date of assessment - Date of 1st IMP + 1. Based on the number of trial days, subjects are mapped to the corresponding trial week. In addition, only last observations within the same mapped weeks are reported in the summary tables by trial week.

Table 5.4-1 Mapped Trial Week Windows for Efficacy Analysis	
Mapped Week	Mapped Trial Day Range^{a,b}
Week 1	Day 1 - Day 7
Week 2	Day 8 - Day 14
Week 3	Day 15 - Day 21
Week 4	Day 22 - Day 28
Week 5	Day 29 - Day 35
Week 6	Day 36 - Day 42
Week 7	Day 43 - Day 49

^a Relative days to the first day of IMP.

^b Evaluations occurring more than three days after the last dosing date will be excluded from the analyses.

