8.1.1 Primary Efficacy Analyses

The primary endpoint with the treatment of centanafadine is the four-week continuous abstinence rate of subjects during Week 4 to Week 7. A participant is considered abstinent from combustible cigarettes if he or she self-reports tobacco abstinence (no cigarette smoking, not even a puff) assessed by responses to daily messages throughout the period and has an exhaled CO level of less than 5 ppm using the Vitalograph Breath CO monitor in the office at scheduled Week 5 and Week 7. An intent-to-treat approach is

Protocol 405-201-00055 Statistical Analysis Plan

taken in which any participants lost to follow-up / early termination after receiving the IMP, or who have smoked during Week 4 to Week 7 will be counted as non-abstinent.

Primary endpoint calculation:

- Set it as four-week continuous abstinence:
 - If there is no smoking in the self-report.
 - And if subject has exhaled CO level of less than 5 ppm using the Vitalograph BreathCO monitor in the office at scheduled Week 5 or Week 7 value is missing.
 - And if subject has exhaled level of less than 5 ppm using the Vitalograph BreathCO monitor in the office at scheduled Week 7.
 - Missing value check:
 - For CO value, only one missing value is allowed, and Week 7 value cannot be missing.
 - For self-report value, only one missing in each visit Week (7 days) is allowed. The missing value is checked per each week.
- All the others will be set as non-abstinent.
 - Week 7 CO value is missing
 - Two or more missing in self-report in each visit week (7 days)
 - Lost to follow-up/Early termination
 - Subjects with actual data that they were smoking. (CO value \geq 5 ppm or any smoking record in self-report.)

A descriptive statistic will be provided for the continuous smoking abstinence rate during Week 4 to Week 7 with 90% binomial confidence intervals. For all binomial confidence intervals, it is based on normal approximation. If the number of abstinent or the number of non-abstinent ≤ 5 , we will use the exact method.

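### The protocol contradicts itself on when daily smoking messages stop; if they stop at V6, a permitted early V6 can turn an abstinent participant into a primary-endpoint failure

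*Protocol*

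**What the plan says.** **When messages end.** The heading of Protocol 6.7.2 is "Daily Message (Visit 2 through V6"). In the schedule of events (Protocol Table 6), the row "Smoking Status (via daily messages") is marked up to V6 and has no mark at safety follow-up. Protocol 6.5.16.10 differs: "Electronic messages will be sent to participants starting after the second visit (V2), through the End of Study". The Explanation of Terms says that End of Study "is defined as the date of safety follow-up or the date of early termination", and Protocol 6.6.8 puts that follow-up 7 to 10 days after V6.

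**When V6 happens.** SAP 3.1 places the last visit "seven weeks (± 3 days) after starting the study drug (Week 7 visit V6"). Protocol 4.9.3 allows early attendance: "Participants may attend sessions up to three calendar days pre or post the scheduled visit".

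**How Week 7 is scored.** SAP 5.4 numbers days by "Trial Day = Date of assessment - Date of 1st IMP + 1", so the first dose is Day 1, and Table 5.4-1 fixes Week 7 at Days 43 to 49. SAP 8.1.1 tolerates one missing self-report per week. Its list of non-abstinent conditions includes "Two or more missing in self-report in each visit week (7 days"). The SAP does not say how to treat a day on which no message was sent.

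**The concern.** The primary endpoint needs a daily record for every day of Weeks 4 to 7. On one reading of the protocol, that record stops at an appointment that may fall before Week 7 ends. A participant who answered every message with no smoking, and whose CO was below 5 ppm at Weeks 5 and 7, could then fail the missing-report check only because the visit was booked early. The error runs in one direction, lowering the abstinence rate that is to be set against the 50% varenicline benchmark (Protocol 1.1). It would also make a participant's success depend on scheduling.

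**Working it through.** The plan states no figure for this, so the check is a day count.

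**Inputs**
- Week 7 is Days 43 to 49 (SAP Table 5.4-1).
- One missing report per week is allowed in the primary analysis (SAP 8.1.1), two in Sensitivity Analysis II (8.1.3) and three in III (8.1.4). Sensitivity Analysis I (8.1.2) treats all missing values as no smoking.
- Nominal V6 day: seven weeks after the first dose is Day 50 under the SAP formula (49 + 1). Protocol 6.6.3 treats one week on drug as six days after starting, which is Day 7; by analogy V6 would be Day 49. The permitted range is Days 47 to 53 if nominal Day 50, or Days 46 to 52 if nominal Day 49.
- The message sent on the V6 day is counted as answered. Protocol 4.9.4 keeps the response window open until the next message.

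**Formula**, if messages stop at V6 and unsent days count as missing: missing Week 7 reports = max(0, 49 − V6 day).

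| V6 day | Missing | Primary | Sens. II | Sens. III | Permitted if nominal Day 49 | Permitted if nominal Day 50 |
|---|---|---|---|---|---|---|
| 49 | 0 | passes | passes | passes | yes | yes |
| 48 | 1 | passes, allowance used up | passes | passes | yes | yes |
| 47 | 2 | fails | passes | passes | yes | yes |
| 46 | 3 | fails | fails | passes | yes | no |

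If the V6-day message is not counted, each row has one more missing report, and failure then starts at Day 48.

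**If messages run to the End of Study**, no Week 7 report is structurally missing at any permitted V6 date. Footnote b of Table 5.4-1 drops evaluations more than three days after the last dose, so it needs a check. With V6 and the last dose both on Day 46, Day 49 is three days later and is kept. With the last dose on Day 45, Day 49 is four days later and is dropped; that is one missing report, which the primary rule tolerates but which uses up the allowance.

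**Size.** One abstainer rescored is 1/50 = 2 percentage points. If a share f of true abstainers has V6 on a failing day, the expected rate is p × (1 − f). The documents do not give f, so these values are assumptions:

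| True rate p | f = 5% | f = 10% | f = 20% |
|---|---|---|---|
| 50% | 47.5% | 45.0% | 40.0% |
| 65% | 61.8% | 58.5% | 52.0% |

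If V6 dates were spread evenly over the seven permitted days, f would be 1/7 (nominal Day 50, Day 47 failing) or 2/7 (nominal Day 49, Days 46 and 47 failing). A true 50% would then become 0.50 × 6/7 = 42.9% or 0.50 × 5/7 = 35.7%. An even spread is also an assumption.

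For V6 on Day 48, suppose each message sent has a 5% chance of being missed (assumed). The chance of failing the Week 7 check rises from P(at least 2 of 7) = 1 − 0.95^7 − 7 × 0.05 × 0.95^6 = 4.4% to P(at least 1 of 6) = 1 − 0.95^6 = 26.5%.

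**The case against.** The strongest reply is that the loss depends on three readings that the documents leave open.

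1. **Messages may not stop at V6.** Protocol 6.5.16.10 continues them to safety follow-up, and 6.5.16.9 says the same of the compliance messages. The V6 column of Table 6 is headed Week 6 to Week 7, so its mark could mean messages through Week 7. This stands, and it is why the defect is a contradiction rather than a settled stop date. It does not remove the problem, because 6.5.16 is not clearly the controlling text. It starts smoking messages after V2, whereas 6.6.1, 6.7.1 and Table 6 start them after screening. It also runs compliance messages past the visit at which all unused drug is returned. A site that set up the app from 6.7.2 would stop at V6.
2. **The nominal V6 day is not fixed.** This also stands. On the literal Day 50 reading, Day 46 is not permitted, two days early (Day 48) passes, and only Day 47 fails.
3. **Unsent may not mean missing, and a visit week may not be the fixed week.** The SAP states neither point. However, Table 5.4-1 is its only week definition for efficacy, Weeks 4 and 6 have no clinic visit to anchor a week, and nothing exempts unsent days. A programmer following the text would probably count them as missing.

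A reader might infer that every participant seen two or three days early is scored non-abstinent, or that the four-week window cannot be completed. The documents do not support either claim. Even on the adverse reading, with the V6-day message counted, five or six of the seven permitted V6 dates avoid automatic failure.

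**Conclusion.** The contradiction over the message end date is real and bears directly on who counts as a primary-endpoint success. The misclassification is conditional: it needs messages to end at V6, Week 7 to be the fixed Days 43 to 49, and unsent days to count as missing. Under those conditions, and with the V6-day message counted, a V6 on Day 47 fails an abstinent participant under either day convention. Day 46 fails only where it is a permitted date, and Day 48 leaves no room for an ordinary missed reply.

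The firm size is 2 points per abstainer lost at n=50, always downward. The expected rates under assumed visit spreads and miss rates only illustrate scale; they are not estimates of bias in this trial.

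The sensitivity analyses do not repair the primary result. With the V6-day message counted, Analysis I recovers all these participants, II only those with two missing, and III those with up to three. Each does so by loosening the rule for everyone. The point should be settled before the endpoint is derived.

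**What to change.** - **Protocol:** reconcile 6.5.16.10, 6.7.2 and Table 6 so that smoking-status messages run to Day 49 or V6, whichever is later. State V6's nominal trial day.
- **SAP 8.1.1, 8.1.3, 8.1.4, 8.3.6 and 8.3.8:** count a self-report as missing only if a message was due that day. This also protects any participant whose messages were in fact switched off at V6.
- **SAP Table 5.4-1, footnote b:** state that the exclusion more than three days after the last dose does not turn Week 7 self-reports after an early V6 into missing ones.

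The cost is a setting in the messaging app already in use, one protocol clarification and a few SAP sentences. A few participants would answer up to three more messages after V6. If only the SAP wording were changed, up to three of the 28 days (4 × 7) would go unobserved for those participants, so the message end date should be settled as well.
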